4.1. Protocol Deviations

Important protocol deviations (including deviations related to study inclusion/exclusion criteria, conduct of the trial, patient management or patient assessment) will be summarised and listed.

Protocol deviations will be tracked by the study team throughout the conduct of the study in accordance with the Protocol Deviation Management Plan [Version 3, dated 16-JUN-2021].

- Data will be reviewed prior to locking the database to ensure all important deviations are captured and categorised on the protocol deviations dataset.
- This dataset will be the basis for the summaries and listings of protocol deviations.

A separate summary and listing of all inclusion/exclusion criteria deviations will also be provided. This summary will be based on data as recorded on the inclusion/exclusion page of the eCRF.

5. CONSIDERATIONS FOR DATA ANALYSES AND DATA HANDLING CONVENTIONS

5.1. Study Treatment & Sub-group Display Descriptors

Data Displays for Reporting ^[1]			
Code	Description		Order in TLF
A	Part 1: Dose Escalation	GSK2857916 2.5 mg/kg + Pembrolizumab 200 mg Escalation	1
B		GSK2857916 1.92 mg/kg + Pembrolizumab 200 mg Escalation ^[2]	2
C		GSK2857916 3.4 mg/kg + Pembrolizumab 200 mg Escalation	3
D	Part 2: Dose Expansion	GSK2857916 2.5 mg/kg + Pembrolizumab 200 mg Expansion	4
E	Part 2: Futility Interim Analyses ^[3]	GSK2857916 2.5 mg/kg + Pembrolizumab 200 mg Escalation	5
F		GSK2857916 2.5 mg/kg + Pembrolizumab 200 mg Expansion	6
G		GSK2857916 2.5 mg/kg + Pembrolizumab 200 mg Overall	7
H	Part 1 and Part 2	GSK2857916 2.5 mg/kg + Pembrolizumab 200 mg Overall	8

Notes:

^[1] No treatment assignment schedule nor randomization schedule is planned for this multi-part, single-arm, open label study.

^[2] Dose level 1.92 mg/kg may be tested if dose level 2.5 mg/kg is not cleared.

^[3] These treatment codes will be applied for futility interim analyses (IA) in part 2 only

5.2. Baseline Definitions

For all endpoints (except as noted in baseline definitions) the baseline value will be the latest pre-dose assessment with a non-missing value, including those from unscheduled visits. If time is not collected, Day 1 assessments are assumed to be taken prior to first dose and used as baseline. If no central lab value is available, the latest non-missing pre-dose value from local lab will be used. If there are multiple assessments on the same day, the mean will be used as the baseline value.

Unless otherwise stated, if baseline data is missing no derivation will be performed and baseline will be set to missing.

5.3. Examination of Covariates, Other Strata and Subgroups

5.3.1. Examination of Subgroups

The list of subgroups may be used in descriptive summaries and statistical analyses. Additional subgroups of clinical interest may also be considered.

- If the percentage of subjects is small within a particular subgroup, then the subgroup categories may be refined.
- If the category cannot be refined further, then descriptive rather than statistical comparisons may be performed for the particular subgroup.

Subgroup	Categories
Age	18 to <65, 65 to <75, >=75
Sex	Male, Female
Ethnic Background	White, Other
ISS Staging at Screening & at Initial Diagnosis	I, II, III, Other (Unknown or Missing)
Number of prior lines of therapy	<=3,4-5, >5
Type of myeloma	IgG, Non-IgG
Extramedullary disease	No, Yes, Missing
Refractory to prior anti-cancer therapy	
 • Any Proteasome Inhibitor (PI) 
 ○ Bortezomib ○ Carfilzomib ○ Ixazomib • Any Immunomodulator (IMiD) 
 ○ Thalidomide ○ Lenalidomide ○ Pomalidomide • Monoclonal Antibodies 
 ○ Anti-CD38 [2] ○ Anti-CD38 in combination [3] • PI+IMiD • Anti-CD38+PI+IMiD • Penta-refractory [4]

Subgroup	Categories
Cytogenetics Risk ^[1]	High, Other (non-high risk, not done, or missing)
Prior anti-cancer therapy of interest	
 With prior Anti-CD38 Treatment and IMiD and Proteasomes Inhibitors. Without prior Anti-CD38 Treatment. With prior IMiD and Proteasomes Inhibitors. With prior Anti-BCMA, Anti-CD38, or Daratumumab Treatment
Renal Impairment per eGFR (mL/min/ 1.73 m ²)	
 Normal: >=90, Mild: >=60, <90, Moderate: >=30, <60, Severe: 0, <30, Missing

NOTES:

- ^[1] A subject is considered as high risk if the subject has any of at least of the following cytogenetics: t(4;14), t(14;16), and 17p13del ([Kastritis, 2017](#)).
- ^[2] Defined as prior CTX regimen with Anti-CD38 (i.e. Daratumumab, Isatuximab) as the only drug.
- ^[3] Defined as prior CTX regimen with Anti-CD38 (i.e. Daratumumab, Isatuximab) and other drugs.
- ^[4] Defined as refractory to: Bortezomib, AND Carfilzomib AND Lenalidomide AND Pomalidomide AND Daratumumab.

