16.11.6. Efficacy Figures

Efficacy: Figures					
No.	Population	IDSL / Example Shell	Title	Programming Notes	Deliverable [Priority]
Response					
2.001	All Treated	Programming Note	Forest Plot – Overall Response Rate (ORR) Based on Investigator-Assessed Response	Report for Part 1 and Part 2, and combined Part 1 and Part 2: Similar to Figure 12.012 in BMA117159 (primary_02).	P-SAC [3], F-SAC [4]
2.002	All Treated	RE8b	Investigator Assessed Maximum Percent Reduction from Baseline in M-Protein (or FLC) Measurement	Report for: Part 1, Part 2, and combined Part 1 and Part 2; Summarize by: dose level (Refer to Section 5.1 for ordering of dose level and omit 1.92 mg/kg if data is not available) Total. Refer to mid205678 (primary_01) Figure 2.0030 for guidance	P-SAC [3], F-SAC [4]
Time-to-Event Endpoints					
2.003	All Treated	TTE10	Graph of Kaplan Meier Survival Curves for Duration of Response (GSK2857916 2.5 mg/kg)	Report for: 2.5 mg/kg doses only; Refer to Section 5.1 and use only code A, code D, and code H for dose level;	P-SAC [3], F-SAC [4]
2.004	All Treated	TTE10	Graph of Kaplan Meier Survival Curves for Time to Response (GSK2857916 2.5 mg/kg)	Report for: 2.5 mg/kg doses only; Refer to Section 5.1 and use only code A, code D, and code H for dose level;	P-SAC [3], F-SAC [4]
2.005	All Treated	TTE10	Graph of Kaplan Meier Survival Curves for Time to Best Response (GSK2857916 2.5 mg/kg)	Report for: 2.5 mg/kg doses only; Refer to Section 5.1 and use only	P-SAC [3], F-SAC [4]

Efficacy: Figures					
No.	Population	IDSL / Example Shell	Title	Programming Notes	Deliverable [Priority]
				code A, code D, and code H for dose level;	
2.006	All Treated	TTE10	Graph of Kaplan Meier Survival Curves for Progression Free Survival (GSK2857916 2.5 mg/kg)	Report for: 2.5 mg/kg doses only; Refer to Section 5.1 and use only code A, code D, and code H for dose level;	P-SAC [3], F-SAC [4]
2.007	All Treated	TTE10	Graph of Kaplan Meier Survival Curves for Time to Progression (GSK2857916 2.5 mg/kg)	Report for: 2.5 mg/kg doses only; Refer to Section 5.1 and use only code A, code D, and code H for dose level;	P-SAC [3], F-SAC [4]
2.008	All Treated	TTE10	Graph of Kaplan Meier Survival Curves for Overall Survival (GSK2857916 2.5 mg/kg)	Report for: 2.5 mg/kg doses only; Refer to Section 5.1 and use only code A, code D, and code H for dose level;	P-SAC [3], F-SAC [4]

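### The cytogenetic-risk subgroup pools untested and missing results with tested non-high risk, so its comparison row does not describe standard-risk disease (minor, exploratory)

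*SAP*

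**What the plan says.** The subgroup table in SAP Section 5.3.1 defines the cytogenetic levels as "High, Other (non-high risk, not done, or missing". Its first footnote ties the High level to t(4;14), t(14;16) or 17p13del: "A subject is considered as high risk if the subject has any of at least of the following cytogenetics". A subject with no result cannot meet that definition and so falls into Other.

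Other rows of the table treat unknown status differently:
- Extramedullary disease: "No, Yes, Missing".
- ISS stage: "I, II, III, Other (Unknown or Missing", so Other there holds no subject of known stage.
- Renal impairment by eGFR: Missing is a level of its own.

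The status of the list is permissive: "The list of subgroups may be used in descriptive summaries and statistical analyses". There is one clause for changing categories: "If the percentage of subjects is small within a particular subgroup, then the subgroup categories may be refined". It responds to small size, not to unknown status.

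Section 16.11.6 plans Figure 2.001, "Forest Plot – Overall Response Rate (ORR) Based on Investigator-Assessed Response", for the primary and final analyses. The entry does not name the subgroup rows; it refers to a figure from another study.

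**The concern.** Other combines two kinds of subject: those tested with no high-risk abnormality, and those whose risk is not known. Some of the second kind may carry one of the listed abnormalities. If ORR is lower in high-risk disease, they pull the Other estimate down towards the High estimate, and the regimen looks less dependent on cytogenetic risk than it is. Even with no numerical bias, a reader of an ORR display by this subgroup could not tell how many subjects in the row were tested and negative, so the row describes no defined clinical group.

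What is at stake is the reading of one exploratory, descriptive comparison. No other section of the SAP separates the groups for subgroup analysis or adds a sensitivity analysis.

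**Working it through.** **The plan's own figures.** The SAP gives no figure for the cytogenetic subgroup. Its only ORR design figures are those of the Part 2 futility design (Section 3.1.2.1). An exact binomial recursion over the Table 3 boundaries, with success above 14 of 28, gives a type I error of 0.0997 (stated 0.10), power of 80.55% (stated 80.6%) and early termination of 86.1% and 15.5% (stated 86.1% and 15.6%). The expected sample sizes come out about one lower than stated (19.1 and 27.0 against 20 and 28), which has no bearing here. Cytogenetic category does not enter this design.

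**Inputs for the dilution.**
- pH, ORR in high risk: 40%, and pN, ORR in non-high risk: 60%. These borrow the null and alternative values of Section 2.4.2 as illustrations; the SAP does not assign them to risk groups.
- u, share of subjects with unknown risk: 10-40%, assumed.
- h, true high-risk prevalence, the same in tested and untested subjects: 20-40%, assumed.
- Within each risk class, untested subjects respond like tested ones: assumed.

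**Formulas.**
- ORR in unknown subjects: pU = h·pH + (1−h)·pN
- ORR in Other: pO = [(1−u)(1−h)·pN + u·pU] / [(1−u)(1−h) + u]
- Share of the contrast retained: (pO − pH)/(pN − pH) = 1 − u·h / [(1−u)(1−h) + u]

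The last form shows that the retained share does not depend on the two ORRs chosen.

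**One case in full** (u = 20%, h = 30%): pU = 0.3×0.40 + 0.7×0.60 = 0.54. pO = (0.56×0.60 + 0.20×0.54)/0.76 = 0.584. The contrast is 18.4 points instead of 20, so 92% is retained.

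**Range, with a true contrast of 20 points.**

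| u | h = 20% | h = 30% | h = 40% |
|---|---|---|---|
| 10% | 19.5 | 19.2 | 18.8 |
| 20% | 19.0 | 18.4 | 17.6 |
| 30% | 18.6 | 17.7 | 16.7 |
| 40% | 18.2 | 17.1 | 15.8 |

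The retained share runs from 97.6% (u = 10%, h = 20%) to 78.9% (u = 40%, h = 40%).

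**If untested subjects differ in risk from tested ones** (u = 20%, h = 30% among the tested): if all untested subjects are high risk, pO = (0.56×0.60 + 0.20×0.40)/0.76 = 0.547, a contrast of 14.7 points (74% retained). If none are, the contrast stays at 20 points.

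**Against sampling error.** Exact 95% intervals for illustrative counts that add to 28 subjects: 3 of 8 gives 8.5% to 75.5%, and 12 of 20 gives 36.1% to 80.9%. A shift of 0.5 to 4.2 points in Other is small beside these.

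**High row.** It needs a detected abnormality, so its membership and its ORR are the same with or without the pooling.

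**The case against.** The strongest objection is statistical: with so few subjects, pooling can give the more accurate estimate of the contrast. Assume ORRs of 35% and 60%, 7 High and 21 Other, with 8 of the 21 untested (35% of them truly high risk) or 12 untested (40%).
- Other ORR is (13×0.60 + 8×0.5125)/21 = 56.7%, or (9×0.60 + 12×0.50)/21 = 54.3%. The bias is 3.3 or 5.7 points.
- The standard error of the pooled difference is √(0.35×0.65/7 + 0.567×0.433/21), about 21 points, and the same in the second case. Root mean squared error is about 21 to 22 points.
- With only the 13 or 9 tested subjects as comparators, there is no bias, but the standard error is √(0.35×0.65/7 + 0.60×0.40/13) = 22.6 or √(0.35×0.65/7 + 0.60×0.40/9) = 24.3 points.

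This holds numerically. It does not defeat the point for a descriptive display, because a third row discards no data and the pooled figure can be rebuilt from it. A confidence interval shows imprecision; it does not show misclassification.

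Other objections stand and limit the point. The label states openly what Other contains, so this is a weak category choice and not a mislabelling. Use of the list is optional, and no cytogenetic ORR test is fixed. Ethnic background and type of myeloma also have no separate missing level, so cytogenetics is unusual only among the rows that say how unknowns are handled.

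A reader might infer that the forest plot is the only place where low activity in high-risk disease could be seen. The SAP does not support that: the High row is unaffected, and Listing 1.0013 (Section 16.11.14) shows each subject's response together with cytogenetics at screening. Nor does the SAP establish that Figure 2.001 carries this subgroup, or that Table 1.0026 (Section 16.11.4) uses the pooled categories.

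**Conclusion.** The point holds as a minor one. Section 5.3.1 merges unknown with tested non-high-risk cytogenetics, gives no reason, and departs from three other rows of its own table. Where the subgroup is used for ORR, Other is not a standard-risk estimate. The High-versus-Other contrast is attenuated if some untested subjects are truly high risk and ORR differs by risk.

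The size cannot be fixed from the SAP. Under the assumed ranges the contrast loses about 2% to 21% of its value, or 0.5 to 4.2 points of an illustrative 20. If every subject was tested, it loses nothing.

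A reader might take this as a threat to the trial's main conclusion. It is not: the primary ORR analysis, its type I error and power, and the futility boundaries do not use the category.

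**What to change.** Replace the two levels in Section 5.3.1 with three:
- **High**: any of the three listed abnormalities detected.
- **Non-high risk**: tested for all three, none detected.
- **Not done, incomplete or missing**: everyone else. This also places subjects tested for only some of the abnormalities with none found, whom the footnote does not address.

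Show all three, with counts, in any ORR display by cytogenetic risk, including Figure 2.001 if it carries this subgroup. The pooled Other row may be kept as a supplement.

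The cost is one line of SAP text and one display row. The non-high-risk group becomes smaller and its interval wider.

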5.4. Other Considerations for Data Analyses and Data Handling Conventions

Other considerations for data analyses and data handling conventions are outlined in the appendices:

Section	Component
Section 16.3	Appendix 3 : Assessment Windows
Section 16.3	Appendix 4 : Study Phases and Treatment Emergent Adverse Events
Section 16.5	Appendix 5 : Data Display Standards & Handling Conventions
Section 16.6	Appendix 6 : Derived and Transformed Data
Section 16.7	Appendix 7 : Reporting Standards for Missing Data
Section 16.8	Appendix 8 : Values of Potential Clinical Importance

6. STUDY POPULATION ANALYSES

6.1. Overview of Planned Study Population Analyses

The study population analyses will be based on the “All Treated” population, unless otherwise specified.

Study population analyses including analyses of subject’s disposition, protocol deviations, demographic and baseline characteristics, prior and concomitant medications, disease characteristics at initial diagnosis and at screening, prior and follow-up anti-cancer therapy, surgical/medical procedures, substance use, duration of follow up, exposure and treatment compliance will be based on GSK Core and Oncology Data Standards. Details of the planned displays are presented in [Appendix 11: List of Data Displays](#).

6.2. Disposition of Subjects

A summary of the number of subjects in each of the analysis populations described in [Section 4](#) will be provided (for final analysis, Evaluable population will not be included). In addition, the number of subjects enrolled by centre will be summarized by dose level using the “Enrolled” population. A listing of subjects excluded from each study population will also be provided (for primary analysis, Evaluable population will not be included) using the following rationales for exclusions.

Population	Rationale for Exclusion
All Treated	
 Enrolled into study, but did not receive study treatment(s)
COVID-19	
 Received study treatment(s), but are not suspected, probable, or suspected COVID-19 case diagnosis
DLT Evaluable	
 Enrolled in Part 1 and received study treatment(s), but did not meet the DLT evaluable criteria
All Evaluable	
 Received study treatment(s), but did not meet the All evaluable criteria
Pharmacokinetic (PK)	
 Received study treatment(s), but did not have at least one PK sample obtained
Pharmacodynamic (PD)	
 Received study treatment(s), but did not have at least one biomarker sample obtained

A summary of subject status and reason for study withdrawal will be provided. This display will show the number and percentage of subjects who withdrew from the study, including primary reasons for study withdrawal. Reasons for study withdrawal will be presented in the order they are displayed in the eCRF.

A summary of study treatment status will be provided. This display will show the number and percentage of subjects who are ongoing or discontinued study treatment and a summary of the primary reasons for discontinuation of study treatment. Reasons for study treatment discontinuation will be presented in the order they are displayed in the eCRF. A listing of study treatment discontinuation will be generated. The listing will include last dose date, and reasons for study treatment discontinuation.

6.3. Demographic and Baseline Characteristics

The demographic characteristics (e.g., age, race, ethnicity, sex, baseline height, and baseline body weight and baseline BMI) will be summarized. Age, height, weight and BMI will be summarized using the mean, standard deviation, minimum, median, and maximum. The count and percentage will be computed for sex and ethnicity.

Race and racial combinations will be summarized.

Disease history and characteristics (e.g. time since initial diagnosis in years, date of initial diagnosis) at initial diagnosis and screening will be listed. Separate summaries of disease characteristics at initial diagnosis and screening will be provided. Disease characteristics at screening, including stage, type of multiple myeloma, myeloma light chain and myeloma immunoglobulin, extramedullary disease, lytic bone lesion, renal impairment per eGFR, and genetic characteristics (including high cytogenetic risk) will be summarized and listed.

Medical conditions collected at screening will be summarized by past and current separately.

Substance use, including smoking history and alcohol use will be summarized. Smoking Pack Years which is calculated as (number of cigarettes smoked per day/20) x number of years smoked will be provided.

Prior anti-cancer therapy will be coded using GSK Drug coding dictionary, then summarized by type of therapy and listed. A listing of prior anti-cancer therapy will show the relationship between ATC Level 1, Ingredient, and verbatim text. A summary of the number of prior anti-cancer therapy regimens will also be produced.

Prior anti-cancer therapy for multiple myeloma subjects will also be summarized by type of therapy, and drug class. A summary of multiple myeloma subjects' refractory to prior anti-cancer therapy by drug class will be provided.

Anti-cancer radiotherapy will be listed. Prior cancer and non-cancer related surgeries will be summarized. Prior and on treatment cancer and non-cancer related surgeries will be listed.

6.4. Treatment Compliance

Summaries of study treatment exposure and dose modifications (e.g., number of dose reductions, number of dose interruptions) will further characterize compliance. These analyses are described in Section [6.4.1](#) 'Extent of Exposure'.

6.4.1. Extent of Exposure

Extent of exposure to belantamab mafodotin and pembrolizumab will be summarized and listed separately for each component.

The number of cycles administered to study treatment will be summarised with mean, median, standard deviation, minimum, and maximum.

Dose delivered per cycle (mg/kg/cycle) will be summarized using mean, median, standard deviation, minimum, and maximum by cycle and overall.

- the dose intensity for belantamab mafodotin (mg/kg/3 weeks) which is calculated as the actual cumulative dose (mg/kg) divided by expected duration of exposure in 3 weeks (last infusion date – first infusion date + 21)/21
- the dose intensity for pembrolizumab (mg/3 weeks), which is calculated as the actual cumulative dose (mg) divided by expected duration of exposure in 3 weeks (last infusion date – first infusion date + 21)/21

A by subject summary listing of data on exposure to all study treatments will be produced.

Dose reductions will be summarised by number of reductions and reasons for reductions. Infusion interruptions will be summarised by number of interruptions and reasons for interruptions. Dose delays will be summarised by number of delays and delay duration (days). The number and percentage of the delays for intervals of 1-21, 22-42 and >42 days will be computed. Primary reasons for dose reductions and infusion interruptions will also be summarized by cycle.

Duration of delays is defined as period from the expected start date of dose to actual start date of current dose. Calculation: (actual start date of current dose - expected start date of dose). Expected start date of dose = actual start date of previous dose + 21. Because the protocol allows a window of \pm 3 days for administration of study treatment after Cycle 1, a dose will only be considered delayed if it is 4 or more days after the scheduled dose date.

The summaries of dose modifications will be provided. A plot showing the number and percentage of subjects treated at different dose levels over time will be provided.

The duration of exposure to study treatment (from first day to last day of treatment) will be calculated and summarized using mean, median, standard deviation, minimum, and maximum. A horizontal bar graph of duration of treatment will be produced that displays duration of treatment in months for each subject.

6.5. Concomitant Medications

Concomitant medications will be coded using GSK Drug coding dictionary and summarized. The summary of concomitant medications will show the number and percentage of subjects taking concomitant medications by Ingredient. Multi-ingredient products will be summarized by their separate ingredients rather than as a combination of ingredients. Anatomical Therapeutic Chemical (ATC) classification Level 1 (Body System) information will be included in the dataset created but will not appear on the summary.

In the summary of concomitant medications, each subject is counted once within each unique ingredient. For example, if a subject takes Amoxycillin on two separate occasions, the subject is counted only once under the ingredient “Amoxycillin”. In the summary of concomitant medications, the ingredients will be summarized by the base only, using CMBASECD and CMBASE. Note: In order to be considered a concomitant medication, the concomitant medication must have been taken at some point during the on-treatment window.

Blood products or blood supportive care products with onset date within the on-therapy window will be included in the summary Tables. The frequency and percentage of subjects using blood products and blood supportive care products after the start of study medication will be provided. Supporting listings will also be provided.

